5.4 Dose escalation scheme

The planned dose escalation scheme is summarised in Table 1. Additional cohorts may be added to evaluate intermediate dose levels or to evaluate alternative dosing schedules, depending on emerging safety information and/or pharmacokinetic data if available. Non-clinical studies have indicated that efficacy in rat xenograft models occurs at 5 to 10 mg/kg. This equates to a surface-area scaled human dose of approximately 50 to 100 mg. However, the plasma half-life of IgE in rat is considerably shorter than in human (12 hours versus 2 days) (Hanashiro *et al.*, 2001, 2002). Efficacious doses in the rat were associated with plasma rMOv18 IgE levels sufficient to represent at least 50% of total plasma IgE

for several days after each dose. This is expected to result in a prolonged wave of rMOv18 IgE loaded effector cells entering tissues.

It was originally estimated that in humans a dose of 10 to 25 mg/patient would be required to produce a similar effect (dependent on the patient's endogenous IgE levels). A flat dose escalation scheme, and a possible intra-patient escalation scheme, is therefore proposed which rapidly ascends (using single-patient cohorts) to doses likely to compete with endogenous circulating IgE and then proceeds with more patients per cohort as endogenous IgE levels are exceeded.

Table 1: Planned dose escalation scheme (Flat Dosing)

Cohort	Dose level	Planned no. patients/cohort	Actual no. patients/cohort
1	70 µg	1	2
2	250 µg	1	8
3	500 µg	1	6
4	700 µg	1	3
5	1.5 mg	3	3
6	3 mg	3	3
7	6 mg	3	TBC
8	12 mg	3	TBC
9	25 mg	3	TBC
10	50 mg	3	TBC

As of October 2020, recruitment to Cohort 6 (3mg) has been completed and the trial protocol has been amended to allow intra-patient dose escalation (see Section 5.4.1)

Initially, patients were enrolled in cohorts of one patient (Cohorts 1-4; 70 – 700 µg doses of MOv18 IgE) as the planned doses were low (based on a conservative approach to safety) and were considered unlikely to provoke a significant biological response. In case of toxicity at these dose levels, an additional two to five patients could be added to better evaluate safety.

For Cohorts 5-10 (flat dosing) (1.5 - 50 mg doses of MOv18 IgE), three patients will be enrolled per cohort, with an additional three patients added to a cohort if needed for toxicity, as outlined below (Table 2). No further dose escalation is planned after Cohort 10 (i.e. 50 mg will be the top dose evaluated). For Cohorts 7-9 (intra-patient escalation), a minimum of 1 patient will be enrolled per cohort (see 5.4.1).

If drug supply permits, one or more cohorts may be expanded up to six patients to further explore the safety and efficacy of MOv18 IgE.

One or more cohorts may be repeated but with administration of prophylactic medication (antihistamine, antipyretic and/or corticosteroid), if considered medically appropriate by the Trial Steering Group (see Section 3.6). Under these circumstances, the prophylactic medication should be given after the skin prick test (before IV administration of MOv18 IgE). Any prophylactic medication will be used within its marketing authorisation.

Before commencement of a new cohort, all patients treated at the previous dose level must have received at least three doses and completed at least three weeks since the first dose. For the second patient in any cohort, the first patient in that cohort must have received at least two doses and been followed for at least 24 hours after the last dose. The second, third and subsequent patients in a cohort (if needed) must not receive their first treatments on the same day. If a patient is withdrawn from the study prior to receiving three doses of study medication without experiencing a DLT or a positive skin prick test, a replacement patient will be added to that dose level.

Decisions on dose escalation will be based primarily on toxicities encountered after the first two doses of MOv18 IgE in each cohort (see Table 2), or the first two doses of cycle 2 for patients undergoing intra-patient dose escalation. However, if available, data on toxicities occurring after later doses will also be taken into consideration. The decision to start a new cohort, and selection of the MOv18 IgE dose for each cohort, will be agreed by investigators and sponsor on review of the toxicities experienced by the preceding cohort during the three-week period from first dosing of each patient. The availability of paired pre-treatment and on-treatment tumour biopsies will also be taken into consideration in decisions on starting a new cohort since paired tumour biopsies are required for all patients.

Based on emerging safety information, prophylactic medication (antihistamine, antipyretic and/or corticosteroid), will be given ahead of the patient's **first and subsequent** infusions if considered medically appropriate by the PI and Sponsor. Under these circumstances, the prophylactic medication should be given after the skin prick test (before IV administration of MOv18 IgE). Any prophylactic medication will be used within its marketing authorisation.

Table 2: Dose escalation decision-making

No. Patients with DLT	Action
0/1 (Cohorts 1-4 only)	Increase to next level
0/3	Increase to next level
1/3	Accrue 3 more pts at same dose level
1/3 + 0/3	Increase to next dose level
1/3 + 1/3*	Stop: recommend previous dose level
1/3 + 2/3*	Stop: recommend a lower dose level
1/3 + 3/3*	Stop: recommend a lower dose level
2/3*	Stop: recommend previous dose level
3/3*	Stop: recommend a lower dose level

*No additional patients will be added to a cohort after a second DLT is observed. Should DLT occur in more than 2/3 or 2/6 patients in a cohort, the previous dose level may not be the most appropriate RP2D.

Note: Dose-independent significant toxicity (anaphylaxis) is not counted as a DLT as shown in Table 2 (above) but may limit recruitment to the trial as a whole as outlined in Section 3.4.2.

5.4.1 Intra-patient dose escalations

The established pattern of predictable and tolerable adverse events in Cohorts 1-6 provides reassurance that accelerated dose escalation could proceed subsequently. Intra-patient dose escalation may be initiated from Cohort 7 onwards in order to evaluate alternative doses, depending on emerging safety information and/or pharmacokinetic data if available. An intra-patient dosing schedule has been proposed as per Table 3.

A dose review meeting will be held following completion of Cycle 1 in Cohorts 7 and above, prior to confirming the intra-patient dose escalation for Cycle 2. Should a patient experience any IMP-related AEs of Grade 2* or higher in Cycle 1, then intra-patient dose escalation will not occur, and the patient will continue to be dosed in Cycle 2 based on the flat dose received in Cycle 1 (See Figure 4).

An additional dose review meeting will be held following completion of Cycle 2 prior to confirming the opening of the next cohort. Should a patient experience any IMP-related AEs of Grade 2* or higher in

Cycle 2, then the decision will be made by TSG based on safety data available to either: expand the Cohort by one patient and repeat Cycle 1 and 2 dose levels, **OR** recruit to the next cohort.

Note: Depending on the outcome of the TSG review where patients have experienced a Grade 2 MOv18 related AE, it may be deemed appropriate to move to the next dose level. Assessment for this will be made on a case by case basis. Grade ≥ 2 rash will generally not preclude intra-patient dose escalation or opening of the next cohort.

If a DLT is experienced in Cycle 1 or Cycle 2, treatment will be withheld until toxicity resolves to baseline or Grade 1. Upon resolution, if appropriate, MOv18 IgE may be recommenced at a lower dose, or the patient may withdraw from study treatment. The cohort will be expanded, and a decision will be made by the TSG whether to expand the cohort by 1 or 2 patients, depending on the nature of the DLT observed (e.g. its nature, grade, expectedness and clinical significance).

Table 3: Planned intra-patient dose escalation scheme

Cohort	Cycle 1 Dose level	Cycle 2 Dose level	No. planned patients/cohort
7 ⁽ⁱ⁾	6 mg	*12mg	1**
8 ⁽ⁱ⁾	12 mg	*20mg	1
9 ⁽ⁱ⁾	20mg	*40mg	1

[figure not shown]
* If required, intermediate dose levels may be explored for the starting dose in Cycle 2, this will be discussed at the dose review meeting and is dependent on the emerging safety profile.

**A minimum of 1 patient will be dosed in each cohort, the final number will be dependent on review of safety data from that dose level.

(i) indicates this is an intra-patient escalation cohort

Figure 4: Intra-patient dose escalation: Example of planned escalation

The TSG to review all data and pay careful consideration to the safety of any current or future patient before making any decisions. Planned escalation may vary from the below based on TSG review of emerging safety data.

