3.3.1 Dose limiting toxicity (DLT)

Dose limiting toxicity is defined as any of the following events occurring in the first 3 weeks of IMP administration that are considered to be probably or highly probably related to MOv18 IgE:

(For dose-independent significant toxicity, see Section 3.3.2)

Non-haematological toxicity

- Any other drug-related non-haematological Grade 3 or 4 toxicity EXCLUDING:
 - Grade 3 or 4 nausea or vomiting, in patients who have not received optimal treatment with anti-emetics
 - Grade 3 or 4 diarrhoea in patients who have not received optimal treatment with anti-diarrhoeals e.g. loperamide and/or codeine
 - Transient Grade 3 biochemical abnormalities that are asymptomatic and considered not to be clinically significant
 - Grade 3 fatigue
- Fatal event

Haematological toxicity

- Grade 4 neutropenia ($ANC < 0.5 \times 10^9/L$) for ≥ 5 days duration *see note
- Febrile neutropenia (fever of unknown origin without clinically or microbiologically documented infection with Grade 3 or 4 neutropenia [$ANC < 1.0 \times 10^9/L$] and fever $\geq 38.5^\circ C$)
- infection (documented clinically or microbiologically) with Grade 3 or 4 neutropenia ($ANC < 1.0 \times 10^9/L$);
- Grade 4 thrombocytopenia (platelets $< 25 \times 10^9/L$)
 - a) for ≥ 5 days *see note, or
 - b) associated with active bleeding, or
 - c) requiring platelet transfusion.

* In the event of a Grade 4 neutropenia or Grade 4 thrombocytopenia, a full blood count must be performed at least five days after the onset of the event to determine if a DLT has occurred. Continue to monitor the patient closely until resolution to Grade 3 or less.

Note that:

- Isolated cutaneous toxicity (urticaria or other skin symptoms/signs) without any associated systemic symptoms or signs and without serum tryptase elevation may not be considered a DLT, if agreed by the Trial Steering Group (TSG) (see Section 3.6 for information regarding the Trial Steering Group). Such patients require premedication (at least for the first subsequent dose) and very close observation if they are given further doses of MOv18 IgE;

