5.4.2 Expansion of dose level(s)

If one instance of DLT (as defined in Section 3.3) is observed in up to three patients, then up to six patients will be treated at that dose. If one out of six patients experience a DLT, dose escalation will continue. If two out of up to six (i.e. between two and six) patients experience a DLT, dose escalation will stop, and this dose will be defined as the maximum administered dose (MAD). At least three more patients will be treated at a dose below the MAD to define the MTD.

If any dose-independent significant toxicities (i.e. Grade >1 anaphylaxis, see Sections 3.3.2 and 3.4.2) occur, then the TSG must meet to discuss whether any further patients can be enrolled. See Section 3.4.2.

In case of uncertainty (e.g. patients with a history of immunological reactions to other agents), one or more additional patients with no apparent predisposing factors may be recruited to a dose level to better evaluate toxicity, if agreed by the TSG.

The MAD could also equal the MTD in the event that dose escalation is stopped before two DLTs are observed at a given dose level, due to the expectation that higher dose levels would be too toxic to administer to patients.

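### The DLT window in Section 3.3.1 closes before the escalated Cycle 2 doses start, which contradicts the escalation rules that rely on DLTs in Cycle 2

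*Protocol*

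**What the plan says.** Section 3.3.1 holds the only DLT definition: "any of the following events occurring in the first 3 weeks of IMP administration that are considered to be probably or highly probably related", meaning related to the study drug. The non-haematological criterion begins "Any other drug-related non-haematological Grade 3 or 4 toxicity EXCLUDING", and rash is not among the exclusions. A separate note covers isolated skin toxicity without systemic features "and without serum tryptase elevation may not be considered a DLT, if agreed by the Trial Steering Group". Nothing in Section 3.3.1 opens a new window at a new dose level.

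Section 5.4.2 builds its expansion and stopping counts on that definition: "If one instance of DLT (as defined in Section 3.3) is observed in up to three patients", up to six patients are treated at that dose.

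Other sections assume that Cycle 2 counts:

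- Section 5.4 bases escalation mainly on toxicity after the first two doses in a cohort, "or the first two doses of cycle 2 for patients undergoing intra-patient dose escalation". The same paragraph then says that the decision to start a new cohort rests on toxicities in the three weeks from each patient's first dose.
- Section 5.4.1 says "If a DLT is experienced in Cycle 1 or Cycle 2, treatment will be withheld until toxicity resolves to baseline or Grade 1". It adds that the cohort will be expanded, with the TSG choosing 1 or 2 patients.
- Section 5.5.1 withholds treatment after a DLT with no limit on when it occurs.

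For related events of Grade 2 or higher in Cycle 2, Section 5.4.1 lets the TSG either "expand the Cohort by one patient and repeat Cycle 1 and 2 dose levels" or recruit to the next cohort. A note adds that Grade 2 or higher "rash will generally not preclude intra-patient dose escalation or opening of the next cohort".

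**The concern.** Intra-patient escalation places each patient's highest dose in Cycle 2, and Table 3 plans one patient per cohort. The event that should trigger expansion is a DLT at that highest dose. If the definition stops counting before that dose is given, the trigger cannot operate on schedule, and the count behind the MTD in Section 3.4.1 (DLT in two of three or two of six patients) has no Cycle 2 input.

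The gap applies to every kind of toxicity. Skin reactions are a foreseeable instance, because Section 3.3 reports that urticaria without systemic symptoms is common with this drug. The rash note also carries none of the conditions that Section 3.3.1 attaches to its skin exemption. At stake is whether, after a severe related toxicity in a single patient of a first-in-human trial, further patients at the same dose levels are required or optional before a higher cohort opens.

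**Working it through.** The plan gives no figure to reproduce, so the check is a dose calendar followed by a comparison of rules.

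**Inputs.** Weekly dosing, three doses per cycle (Sections 3.2 and 5.3). DLT window of three weeks from first dosing, taken as days 1 to 21 (Section 3.3.1). Visit tolerance of 2 days either way (Section 7.2.3, Table 4). Dose levels from Tables 1 and 3. Expansion rules from Section 5.4.1.

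**Step 1, calendar.** Dose k falls on day 1 + 7(k − 1).

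- Cycle 1: days 1, 8, 15. All 3 are inside days 1 to 21.
- Cycle 2: days 22, 29, 36. 0 of 3 are inside.

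**Step 2, tolerances.** At the early edge, dose 4 falls on day 22 − 2 = 20, giving 21 − 20 + 1 = 2 days of overlap. Doses 5 and 6 fall no earlier than days 27 and 34, still outside. Delays widen the gap. The extra Cycle 1 dose allowed by Section 5.4.3 moves the first escalated dose to day 22 + 7 = 29. A full two-week delay under Section 5.5.2 before dose 4 moves it to day 22 + 14 = 36.

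**Step 3, which doses are affected.**

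| Cohort | Cycle 1 dose (inside) | Cycle 2 dose (outside) | Where the Cycle 2 dose next meets a window |
|---|---|---|---|
| 7 | 6 mg | 12 mg | Cycle 1 of Cohort 8 |
| 8 | 12 mg | 20 mg | Cycle 1 of Cohort 9 |
| 9 | 20 mg | 40 mg | nowhere in Table 3 |

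Table 1 levels from Cohort 7 are 6, 12, 25 and 50 mg, so 40 mg is not a flat-dose level either. In Table 3, 12 and 20 mg come under DLT observation only after the next cohort has opened.

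**Step 4, consequence for one severe related Cycle 2 toxicity that meets a Section 3.3.1 criterion and is not exempted.**

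| Reading | Rule in Section 5.4.1 | Extra patients |
|---|---|---|
| Counts as a DLT | expansion required | 1 or 2 |
| Not a DLT because of the window | TSG chooses: expand by one, or next cohort | 1 or 0 |

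**Step 5, chance of triggering required expansion.** Let p be the probability of a qualifying Cycle 2 event in one patient. The protocol gives no value, so p is an assumption. With one patient on schedule, the chance that such an event triggers required expansion is 0 under the literal window. It is 1 − (1 − p) = p if the window restarts: 0.10, 0.20, 0.33 or 0.50 for those assumed values of p.

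**The case against.** The strongest reply is that the specific rule already covers the case. The DLT paragraph in Section 5.4.1 was written for these cohorts, names Cycle 2 and makes expansion mandatory; under the literal window those words would have almost nothing to act on. Section 5.5.1 sets no time limit, and Section 5.3 treats dose-limiting toxicity as a reason to stop at any of the six weekly doses. A sensible TSG would apply the Section 3.3.1 criteria in Cycle 2. This stands as evidence of intent. It rules out inferring that the protocol has settled that Cycle 2 events are not DLTs. It does not supply a Cycle 2 window, and Section 5.4.2 still points back to the unamended definition.

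A reader might also infer that the rash note steers the TSG towards the next cohort. The wording does not go that far: it says only that rash does not usually stand in the way, and the sentence before it calls for case-by-case assessment. Nor does the note contradict the DLT rule in Cycle 1. Section 5.4.3 requires three Cycle 1 doses without a DLT before escalation, and that mandatory rule can be read to prevail over a statement of what is usual.

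Figure 4, which Section 5.4.3 cites for decision making, is not shown. It may give an order of precedence or a Cycle 2 DLT branch, so the absence of either cannot be asserted.

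Finally, there are safeguards: a dose review after Cycle 2, completion of three Cycle 2 doses before another cohort is considered, the delay rule in Section 5.5.2, and use of later toxicities for the RP2D under Section 3.4.1. The TSG may also add patients through Table 3's minimum of one per cohort, through Section 5.4.2 in case of uncertainty, or up to six if supply permits. These lower the risk, but the routes to more patients are discretionary where Section 5.4.1 intends a requirement.

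**Conclusion.** The point holds as an internal contradiction in the visible text and should be fixed. The DLT definition excludes all three planned escalated doses (12, 20 or 40 mg, depending on cohort), with at most 2 days of overlap at the early edge of the visit tolerance. Sections 5.4.1, 5.4 and 5.5.1 presuppose that such events can count. The practical difference is 1 or 2 required extra patients against 0 or 1 at the TSG's choice, for any severe related toxicity that meets the criteria.

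A reader might conclude that a higher cohort will open after an uncounted severe event. The documents support only that it could, because the TSG reviews every case. The rash note is a secondary ambiguity within this gap.

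The conclusion assumes that the three weeks run from first dosing, that Table 3 is followed without intermediate levels, and that Figure 4 does not already define a Cycle 2 DLT period. Confidence is medium because of that figure.

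**What to change.** State in Section 3.3.1 that, for intra-patient escalation cohorts, the DLT criteria apply both to the three weeks from first dosing and to the three weeks from the first dose at the escalated level. Section 5.4.2 then inherits the change through its cross-reference. Make the three-week review period in Section 5.4 match, so that the paragraph agrees with its own reliance on Cycle 2 doses. Check that Figure 4 agrees.

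As a secondary clarification, limit the rash note in Section 5.4.1 to rash that is not a DLT under Section 3.3.1.

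The cost is small. The restarted window (days 22 to 42 on schedule) is the same three weeks as Cycle 2, after which a dose review is already held, so no new waiting period arises unless a DLT occurs. The downside is occasionally 1 or 2 more patients in a cohort and slightly slower escalation.

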5.4.2 Expansion of dose level(s)

If one instance of DLT (as defined in Section 3.3) is observed in up to three patients, then up to six patients will be treated at that dose. If one out of six patients experience a DLT, dose escalation will continue. If two out of up to six (i.e. between two and six) patients experience a DLT, dose escalation will stop, and this dose will be defined as the maximum administered dose (MAD). At least three more patients will be treated at a dose below the MAD to define the MTD.

If any dose-independent significant toxicities (i.e. Grade >1 anaphylaxis, see Sections 3.3.2 and 3.4.2) occur, then the TSG must meet to discuss whether any further patients can be enrolled. See Section 3.4.2.

In case of uncertainty (e.g. patients with a history of immunological reactions to other agents), one or more additional patients with no apparent predisposing factors may be recruited to a dose level to better evaluate toxicity, if agreed by the TSG.

The MAD could also equal the MTD in the event that dose escalation is stopped before two DLTs are observed at a given dose level, due to the expectation that higher dose levels would be too toxic to administer to patients.

5.4.3 Patients enrolled in the intra-patient escalation cohorts

A patient must receive 3 doses of MOv18 IgE without experiencing a DLT in Cycle 1 before they are eligible for intra-patient escalation at a higher dose for Cycle 2. The patient must complete all three doses in Cycle 2 before consideration is given to opening another cohort at a higher dose.

If a patient receives less than 80% of Cycle 1 Dose 1, but tolerates 100% of Doses 2 & 3, the patient will need to receive a full fourth Cycle 1 dose to make them evaluable before consideration of intra-patient dose escalation in Cycle 2. In this situation the treatment course may consist of more than 6 doses.

If a patient has received at least one dose in Cycle 2 but is then withdrawn due to disease progression or other non-clinical reasons prior to completion of treatment, then the TSG will decide whether to expand the current cohort or proceed to the next cohort. This decision will be based on a review of the clinical safety data.

[See Figure 4 “Intra-patient dose escalation” schema for decision making].

5.5 Dose modifications

5.5.1 Dose reductions

Patients experiencing a DLT at any time will have their MOv18 IgE treatment withheld until toxicity resolves to baseline or Grade 1. After resolution, MOv18 IgE may be recommenced at the same dose.

Dose reduction is not generally envisaged but if required (for DLT or other toxicities, other than Grade \geq 2 anaphylaxis) will be to the next lowest dose according to the dose escalation scheme (Table 1). Only one dose reduction is allowed per patient. Individual patient dose reductions should be discussed and agreed with the CDD.

Patients experiencing Grade \geq 2 anaphylaxis (see Appendix 5) must discontinue study medication (see Section 3.3.2 and 3.4.2). As per Section 3.4.2, the TSG will also take into consideration any equivocal or Grade 1 events, should these occur. For other infusion reactions (see Appendix 6), continuation of study drug at the same dose level may be appropriate but must be discussed with the TSG.

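### For intra-patient Cohorts 7(i)–9(i), Section 5.5.1 permits restart at the same dose after a DLT while Section 5.4.1 offers only a lower dose or withdrawal, and the Table 1 reduction step does not fit the 40 mg level

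*Protocol*

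**What the plan says.** Two sections of the Protocol set out what happens to a patient in an intra-patient cohort after a DLT.

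Section 5.4.1, written for these cohorts, states: "If a DLT is experienced in Cycle 1 or Cycle 2, treatment will be withheld until toxicity resolves to baseline or Grade 1". After that, "MOv18 IgE may be recommenced at a lower dose, or the patient may withdraw from study treatment". Restart at the same dose is not among the options.

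Section 5.5.1 applies to any patient with a DLT at any time. It has the same withholding rule but then says "After resolution, MOv18 IgE may be recommenced at the same dose". It presents dose reduction as unusual. Where a reduction is needed, it "will be to the next lowest dose according to the dose escalation scheme (Table 1"), and that table is titled as the flat-dosing scheme. It adds "Only one dose reduction is allowed per patient" and "Individual patient dose reductions should be discussed and agreed with the CDD". The section has no exception for the intra-patient cohorts and does not cite Table 3, which holds their doses.

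Three other provisions matter for the check:

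- Under Section 5.4.3, a patient escalates only after three Cycle 1 doses without a DLT.
- A patient with a related Grade 2 or higher event in Cycle 1 is generally not escalated; then "the patient will continue to be dosed in Cycle 2 based on the flat dose received in Cycle 1" (Section 5.4.1, with exceptions for rash and case-by-case decisions).
- The Table 3 footnote says "If required, intermediate dose levels may be explored for the starting dose in Cycle 2".

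**The concern.** The two sections agree on when to stop and when re-dosing may be considered. They differ on the dose at which the same patient may restart. An investigator who looks under dose modifications finds permission to give again the dose that caused the DLT. An investigator who looks under intra-patient escalation finds only a lower dose or withdrawal. In a first-in-human trial, where the escalated dose is up to twice what the patient had received before, that should not depend on which section is opened.

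The second issue is the target of a reduction. Table 1 contains neither 20 mg nor 40 mg, and both are planned doses in Table 3. A reduction rule that looks only at Table 1 may therefore send a patient to a dose higher than the last one that patient completed without a DLT.

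**Working it through.** No sample size or error rate is involved. The check is a comparison of the two rules and a table look-up.

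**Inputs**

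- Table 1 (Section 5.4), in mg: 0.07, 0.25, 0.5, 0.7, 1.5, 3, 6, 12, 25, 50.
- Table 3 (Section 5.4.1), Cycle 1 / Cycle 2 in mg: 7(i) 6/12; 8(i) 12/20; 9(i) 20/40.

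**Step 1: restart at the same dose after a DLT on the planned escalated dose.** Ratio to the Cycle 1 dose: 12/6 = 2.0; 20/12 = 1.67; 40/20 = 2.0. Section 5.5.1 permits each of these; Section 5.4.1 offers none.

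**Step 2: who must agree to such a restart.** Section 5.5.1 requires agreement of the sponsor's Centre for Drug Development (CDD) for dose reductions. It requires discussion with the Trial Steering Group (TSG) for same-dose continuation after infusion reactions other than Grade 2 or worse anaphylaxis. For a same-dose restart after any other DLT it names neither.

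**Step 3: the reduction step under 5.5.1.** Let N(d) be the largest Table 1 level strictly below d.

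| Cohort | DLT at dose d (mg) | N(d) (mg) | N(d) / Cycle 1 dose |
|---|---|---|---|
| 7(i) | 12 (escalated) | 6 | 6/6 = 1.0 |
| 8(i) | 20 (escalated) | 12 | 12/12 = 1.0 |
| 9(i) | 40 (escalated) | 25 | 25/20 = 1.25 |
| 7(i) | 6 (Cycle 1 dose) | 3 | 3/6 = 0.5 |
| 8(i) | 12 (Cycle 1 dose) | 6 | 6/12 = 0.5 |
| 9(i) | 20 (Cycle 1 dose) | 12 | 12/20 = 0.6 |

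Only the escalated dose in 9(i) misfits. The step from 40 to 25 mg is a cut of 1 − 25/40 = 37.5%, but it lands 25% above the patient's Cycle 1 dose.

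**Step 4: intermediate Cycle 2 doses.** I assume these lie between the Cycle 1 dose and the planned Cycle 2 dose.

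- 7(i), above 6 and up to 12 mg: N(d) = 6, the Cycle 1 dose.
- 8(i), above 12 and up to 20 mg: N(d) = 12, the Cycle 1 dose.
- 9(i), above 20 and up to 25 mg: N(d) = 12, which is 12/20 = 0.6 of the Cycle 1 dose.
- 9(i), above 25 and up to 40 mg: N(d) = 25, which is 1.25 times the Cycle 1 dose.

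In 9(i) the current rule never returns the patient's own 20 mg.

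**Step 5: choice of remedy.** Sending every escalated-dose DLT back to the Cycle 1 dose would be less cautious than the current rule in part of 9(i). From 22 mg it would give 20 mg (a cut of 1 − 20/22 = 9%), and from 25 mg it would give 20 mg (a cut of 20%), where Table 1 gives 12 mg in both cases. Taking the lower of the Cycle 1 dose and N(d) avoids this:

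- 7(i): min(6, 6) = 6.
- 8(i): min(12, 12) = 12.
- 9(i), above 20 and up to 25 mg: min(20, 12) = 12.
- 9(i), above 25 and up to 40 mg: min(20, 25) = 20.

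No result exceeds the Cycle 1 dose, and none is higher than the current Table 1 step.

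**The case against.** A reader might infer that the sections contradict each other so that both cannot be obeyed. The text does not support that. Both clauses are permissive, and an investigator who follows 5.4.1 complies with both. It is also ordinary practice to let the specific section govern the general one. Section 5.4.3 refers the reader to Figure 4 for decision-making in these cohorts, and that figure may settle the matter. What stands is that the visible text nowhere states the precedence, and 5.5.1 carries no exception.

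A reader might also infer that a rechallenge could go unnoticed. That is unlikely. Section 9.2.2 requires every DLT to be reported to the CDD within 24 hours. Under Section 5.4.1 a DLT leads to expansion of the cohort, with the TSG deciding by how many patients, and the text introducing Figure 4 asks the TSG to weigh the safety of current patients. None of this expressly requires agreement before a same-dose restart.

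On the reduction step, 25 mg is lower than 40 mg, so it does not breach 5.4.1, and no rule caps a reduced dose at the last tolerated one. The CDD must agree each reduction and could choose otherwise. The exposure is also short: after a DLT on a Cycle 2 dose, at most two of the three Cycle 2 doses remain, plus up to three maintenance doses if supply permits. These points limit the consequence; they do not make 25 mg a sensible default for that patient.

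Two further provisions bear on the scenario. Section 3.3.1 defines a DLT by the first three weeks of administration, so an event on an escalated Cycle 2 dose falls outside that window. The point relies on the wider use of the term in 5.4.1 (either cycle) and 5.5.1 (any time). Section 5.3 makes the six planned doses conditional on no DLT, but sets no restart dose and so does not resolve the difference.

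**Conclusion.** The point holds in modest form. For Cohorts 7(i)–9(i), 5.5.1 read alone permits rechallenge at the dose that caused the DLT (12, 20 or 40 mg on the planned escalation), while 5.4.1 offers only a lower dose or withdrawal. Separately, the Table 1 reduction from a 9(i) Cycle 2 dose above 25 and up to 40 mg is 25 mg, against 20 mg completed without a DLT, and it uses up the single reduction allowed.

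The reach is small: three cohorts planned at a minimum of one patient each, and only if a DLT occurs and re-dosing is chosen. It would be wrong to infer any effect on the escalation decisions. DLT counting, the design and the sample size are unaffected. The conclusion rests on the visible text, with Figure 4 unseen, and on the Table 3 doses or intermediate Cycle 2 doses within their range. It merits correction because it concerns re-dosing a patient after a DLT and costs almost nothing to cure.

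**What to change.** Add to Section 5.5.1:

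- After a DLT in Cycle 1 or Cycle 2, patients in intra-patient cohorts follow Section 5.4.1: a lower dose or withdrawal, with no restart at the same dose.
- If the DLT occurs on an escalated Cycle 2 dose, the reduced dose is the lower of the patient's own Cycle 1 dose and the next lower Table 1 level. On the planned doses this gives 12 to 6, 20 to 12 and 40 to 20 mg. An intermediate 9(i) dose above 20 and up to 25 mg still goes to 12 mg.
- If the DLT occurs at the Cycle 1 dose, whether in Cycle 1 or in Cycle 2 without escalation, the reduced dose is the next lower Table 1 level: 6 to 3, 12 to 6 and 20 to 12 mg.

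Keep CDD agreement for reductions and leave the flat-dose rule as it is. If Figure 4 already addresses restart after a DLT, check that it agrees. The cost is a few sentences in one section.
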